All colonoscopies will be performed by the endoscopist (trainee and experienced endoscopist) using CAD EYE[®] in detection mode (WLI or LCI), during colonoscopy retrieval. When a suspected polyp is identified by the endoscopist, optical characterization is performed by the endoscopist in WLI and BLI modes, in a first phase and by the CAD EYE[®] with BLI, in a second phase.

Methods plan

Phase 1. Brief virtual chromoendoscopy training on the characterization of colorectal polyps (WLI, LCI and BLI)

Phase 2. CAD EYE[®] system applied during colonoscopy retrieval:

2.1. CAD EYE[®] system OFF: Virtual chromoendoscopy (BLI) – independently characterization of a suspected polyp in WLI and BLI by the first endoscopist and by the second endoscopist (iconographic record)

2.2. CAD EYE® system ON: Characterization mode (BLI): Characterization of a suspected polyp by CAD EYE® and respectively level of characterization (1 to 3) (iconographic record)

Phase 3. Histopathological evaluation (pathologist with gastrointestinal expertise): Resection and recovery of a suspected polyp for anatomopathological characterization

Detailed explanation of Methods phases

Phase 1. Brief virtual chromoendoscopy training on the characterization of colorectal polyps (WLI, LCI and BLI)

Virtual chromoendoscopy training should be performed online through the BASIC e-learning platform (bli.eu/category/e-learning/). This training should be carried out by all participants enrolled in the project (trainees and experienced endoscopists) before its practical application, which will allow skills acquisition on the characterization of virtual chromoendoscopy of colorectal polyps using BLI. Additionally, a brief review of the Kudo classification of pit pattern of colorectal polyps should be carried out.

Phase 2. Evaluation of colorectal polyps in real-time - Optical characterization of colorectal polyps

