The first approach on optical characterization of an identified polyp consists in the evaluation of the polyp, first in WLI mode and then in BLI mode, with CAD EYE® OFF. This evaluation should be systematically performed by two independent endoscopists in the exam room, and the evaluation of both should be recorded on a separate record sheet by the endoscopist who is not performing the examination. The two endoscopists should preferably (but not necessarily) be an experienced endoscopist and a trainee from the last few years, and the presence of at least one experienced endoscopist is mandatory. The independent evaluation is guaranteed by a phased and recorded approach: 1st step - The 1st endoscopist (endoscopist performing colonoscopy) request the polyp evaluation and written record by the 2nd endoscopist (the one who is not performing the colonoscopy) - blinded evaluation because the 1st endoscopist doesn't verbalize his evaluation); 2nd moment - when the 2nd endoscopist signals that he has completed his record, the 1st endoscopist verbally explicit his classification, which is recorded by the 2nd endoscopist. This evaluation should include the histopathological type of polyp (hyperplastic, adenoma, sessile serrated lesion or other type) and the level of confidence of the

evaluation performed (high or low). Kudo classification of pit pattern can also be recorded (optional).

Afterwards, optical characterization mode of CAD EYE® (CAD EYE® ON) in BLI mode should be activated for the evaluation of CAD EYE® optical characterization, in hyperplastic or neoplastic polyps, as well as the level of characterization (graduated from 1 to 3). The evaluation of the CAD EYE® should also be recorded by the endoscopist in the exam room who is not performing the colonoscopy, on its own record sheet.

The iconographic record of evaluated polyps in WLI and BLI modes and the evaluation video using CAD EYE® in BLI characterization mode should be done.

Phase 3. Histopathological evaluation (by pathologist with gastrointestinal expertise)

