After detection and optical characterization of identified colorectal polyps, their resection should be performed by the most appropriate technique according to the size and type of polyp (cold forceps polypectomy if dimensions <3mm), cold snare polypectomy if dimension between 3-10mm and diathermic snare polypectomy/endoscopic mucosal resection if lesions >10mm) and recovery of colorectal polyp for anatomopathological characterization. Each colorectal polyp should be recovered to a separate vial. Unrecovered polyps will not be counted for comparative evaluation of optical characterization.

Statistical analysis

The diagnostic performance of CAD EYE® will be evaluated by comparison with the gold standard (histological characterization in the optical characterization phase), in terms of diagnostic accuracy, sensitivity, specificity, positive predictive value and negative predictive value. Sub-analysis can be performed regarding the size, location and histological type of polyp, as well as the expertise of the endoscopist.

Sample size calculation

For an alpha risk of 0.05 and beta risk of 0.2 for a bilateral test, it will be necessary to include 197 colorectal polyps assuming the initial pre-intervention diagnostic ratio is 0.7 and the final after-intervention ratio is 0.82.

Expected Results

It is expected that the new CAD EYE[®] system will have a diagnostic accuracy in the optical characterization of colorectal polyps around 78.4%, comparable to experienced endoscopists (78.4% vs 79.6%) and superior to less experienced endoscopists (70.7% vs 79.6%).(14) Thus, the new CAD EYE[®] system will allow optical characterization with high accuracy impacting as a decision making tool for the endoscopist in strategies based on optical diagnosis such as "diagnosis and leave behind" for diminutive polyps from sigmoid colon and rectum with high degree of confidence in hyperplastic histology and "predict, resect and discard" for diminutive polyps.

References

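### The sample size does not say whose reading the 0.70 and the 0.82 are; with no endoscopist diagnosis recorded after the CAD EYE output, an aided gain cannot be estimated, and CAD EYE alone is expected at 78.4%, not 82%

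*Combined protocol and SAP*

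**What the plan says.** The Sample size calculation opens "For an alpha risk of 0.05 and beta risk of 0.2 for a bilateral test" and continues that "it will be necessary to include 197 colorectal polyps", assuming that "the initial pre-intervention diagnostic ratio is 0.7 and the final after-intervention ratio is 0.82". It defines neither ratio, names no test, and gives no discordance or correlation between the two readings.

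The readings are set out under Methods plan and in the detailed description of Phase 2. With CAD EYE off (step 2.1) there is "independently characterization of a suspected polyp in WLI and BLI by the first endoscopist and by the second endoscopist", each with a histological type and a high or low confidence. Then: "Afterwards, optical characterization mode of CAD EYE® (CAD EYE® ON) in BLI mode should be activated". From that point the record sheet receives CAD EYE's classification and its level, 1 to 3. Resection and histology follow. No further endoscopist diagnosis is described.

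The first primary objective sets CAD EYE's accuracy against digital chromoendoscopy, and the second sets it against histology. The Statistical analysis section lists accuracy measures for CAD EYE against histology and names no comparative test. Expected Results puts CAD EYE at about 78.4%, similar to experienced endoscopists and better than less experienced ones (70.7%), and concludes that it will have high accuracy "impacting as a decision making tool for the endoscopist".

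**The concern.** A ratio before and a ratio after an intervention would ordinarily be the same reader's diagnosis measured twice. The plan takes the first measurement but not a second one from that reader. The accuracy of CAD EYE alone is a different quantity from the accuracy of an endoscopist who has seen its output, because the endoscopist may reject a correct output or accept a wrong one.

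Two things are at stake. First, it is unclear which contrast 197 polyps are meant to power, and so whether the study has 80% power for the comparison it can make. Second, the closing claim is about the endoscopist's decisions, which are not measured after exposure to CAD EYE.

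**Working it through.** **1. Inputs.** From the Sample size calculation: p1 = 0.70, p2 = 0.82, two-sided alpha 0.05 (z = 1.960), power 0.80 (z = 0.842), n = 197 polyps. From Expected Results: 78.4%, 79.6% and 70.7%. Discordance ψ (the share of polyps on which exactly one of the two readings is correct) is not in the documents and is assumed below.

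**2. Reproducing 197.** Here d = 0.82 − 0.70 = 0.12. If the two readings are independent, ψ = 0.70×0.18 + 0.82×0.30 = 0.126 + 0.246 = 0.372.
- McNemar, Miettinen form: n = [1.960√ψ + 0.842√(ψ − d²(3+ψ)/(4ψ))]² / d² = 197.3.
- McNemar, unconditional form: n = [1.960√ψ + 0.842√(ψ − d²)]² / d² = 200.4.
- Two independent groups, pooled variance: 198 per group.

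The figure of 197 is therefore sound for its stated inputs. It fits either 197 polyps each read twice, with independent readings, or about 197 per independent group. The design, with both readings on one polyp, matches the first.

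**3. Which contrasts can be estimated from the planned record.**

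| Contrast | First reading | Second reading | Estimable? |
|---|---|---|---|
| Unaided endoscopist vs aided endoscopist | recorded (CAD EYE off) | not recorded | no |
| Unaided endoscopist vs CAD EYE alone | recorded (CAD EYE off) | recorded (CAD EYE on) | yes, paired by polyp |
| CAD EYE alone vs histology | recorded (CAD EYE on) | recorded | yes |

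**4. Power at n = 197 if the sized contrast is endoscopist vs CAD EYE alone.** Power = Φ{[d√197 − 1.960√ψ] / √(ψ − d²)}.

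For 70.7% vs 78.4%, d = 0.077. Under independence ψ = 0.707×0.216 + 0.784×0.293 = 0.382. The numerator is 0.077×14.036 − 1.960×√0.382 = 1.081 − 1.212 = −0.131; the denominator is √(0.3824 − 0.0059) = 0.614; Φ(−0.214) = 0.415. The two-group formula with 197 per group gives 0.418.

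The passage in Expected Results is unclear. 79.6% is given first for experienced endoscopists and then appears opposite the 70.7%, where CAD EYE's figure would be expected. The last column therefore takes 79.6% as CAD EYE's accuracy (d = 0.089; ψ = 0.377 under independence).

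| Assumed ψ | 70.7% vs 78.4% | 70.7% vs 79.6% |
|---|---|---|
| independence (0.382; 0.377) | 42% | 53% |
| 0.30 | 51% | 63% |
| 0.20 | 68% | 80% |
| 0.15 | 80% | 90% |

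For 80% power at 70.7% vs 78.4%, the same formula needs 504 polyps under independence, 395 at ψ = 0.30 and 263 at ψ = 0.20.

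**5. If an aided reading were added.** For 0.70 vs 0.82, 197 polyps give 97% power at ψ = 0.20, 87% at 0.30 and 79% at 0.372.

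None of these figures allows for several polyps per patient.

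**The case against.** A reader might infer that the trial collects no data at all on its powered endpoint. The documents do not support that. The text never says that 0.82 belongs to an aided endoscopist. Phase 2 is laid out as CAD EYE off, then CAD EYE on, and the first primary objective compares CAD EYE itself with digital chromoendoscopy. On that meaning both readings exist for every analysed polyp and the contrast can be estimated. This objection stands, although the expected 78.4% for CAD EYE keeps the meaning of 0.82 open.

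It can also be said that no objective concerns aided accuracy, that the decision-tool sentence is an expectation and not an endpoint, and that CAD EYE's predictive values for the two resection strategies remain estimable. All of this is true. It makes an aided reading an addition rather than a repair of a stated objective. It does not rescue the sentence about impact on the endoscopist's decisions, which stand-alone accuracy cannot establish.

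The power shortfall depends on unstated discordance and vanishes if discordance is about 0.15 or lower. That is correct. It arises from the mismatch between 0.82 and the expected accuracy, and not from the absent aided reading. Nor is the arithmetic behind 197 at fault.

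**Conclusion.** The concern holds in a limited form. The sized contrast is undefined. If it is aided versus unaided endoscopist, the gain cannot be estimated, because the second reading is not recorded. If it is unaided endoscopist versus CAD EYE alone, it can be estimated, but the assumed 0.82 conflicts with the protocol's own 78.4%. Power at 197 polyps is then about 42% under independence and 51% to 80% for assumed discordance from 0.30 down to 0.15. With 79.6% as CAD EYE's figure, it is 53% under independence, 63% at 0.30 and 80% at 0.20. On either meaning the planned data do not show an effect on the endoscopist's decisions.

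The power figures assume that 70.7%, the less experienced endoscopists, is the unaided comparator. Against experienced endoscopists, expected at 79.6%, the protocol anticipates no gain.

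**What to change.** **(a) Text changes.**
- State that the sized contrast is the unaided endoscopist (CAD EYE off) versus CAD EYE alone on the same polyp, and say which endoscopist.
- Name a paired test in the Statistical analysis section: McNemar, with allowance for several polyps per patient.
- Reconcile 0.70 and 0.82 with Expected Results, including the two uses of 79.6%.
- Restate the power of 197 polyps across a range of discordance.
- Limit the conclusion to stand-alone accuracy.

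This costs only redrafting, unless the restated power leads the investigators to enlarge the sample.

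**(b) A cheap addition for polyps still to be read.** Record the 1st endoscopist's diagnosis and confidence after the CAD EYE output, with the CAD EYE off entries already locked. Analyse aided versus unaided accuracy as a paired secondary comparison. A 2nd-endoscopist aided reading may be recorded but should be labelled exploratory, because that reader has already heard the 1st endoscopist's classification before CAD EYE is switched on.

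The cost of (b) is a short extra entry per polyp on the existing record sheet; both endoscopists are already in the room. It has two limits. The Brief summary describes the study as under way, so any polyps already read would have no aided reading. An immediate re-read also mixes the CAD EYE effect with that of a second look.
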